## 7.2 Study sites

#### 7.2.1 Study Sites for Aims 1 and 2

Aims 1 and 2: Coordinating Center will collect health system data from Duke University Health System and Vanderbilt University Medical Center, and Medical University of South Carolina, and Wake Forest University Health Sciences via the STAR CRN using CDM.

#### 7.2.2 Study Sites for Aim 3

Aim 3: Duke University Health System, Vanderbilt University Medical Center, Medical University of South Carolina will identify patients and health care providers for interviews; Case Western Reserve University will identify only health care providers for interviews.

Participants will be identified/consented for the qualitative interviews from the following sites:

Duke University Health System (DUHS): Patients & Health Care Providers
 Vanderbilt University Medical Center (VUMC): Patients & Health Care Providers
 Medical University of South Carolina (MUSC): Patients & Health Care Providers

Case Western Reserve University (CWRU): Health Care Providers

## 7.3 Inclusion and exclusion for Aims 1, 2 and 3

#### 7.3.1 Patient EHR data for Inclusion criteria for Aims 1 and 2

- (1) Race equals Black/African-American, American Indian/Alaska Native, Asian, Native Hawaiian/Pacific Islander, or More than one race, and/or Ethnicity equals Hispanic or Latino;
- (2) Documented evidence of HIV positive status (HIV positive diagnosis (ICD10 codes B20-B24, or ICD9 codes 042, V08) and prescription of antiretroviral therapy (ART));
- (3) Documented evidence of elevated AtheroSclerotic CardioVascular Disease risk (ACC/AHA ASCVD 10 year risk ≥5%²⁴, or Framingham Cardiovascular Disease 10 year risk ≥5%²⁵) after HIV diagnosis. The date when the patient first meets either of these CVD risk thresholds and with 1 prior encounter not having CVD risk score defines the **index** time-point for Aim 1 of this study. These risk calculations depend on sex, age, body mass index, diabetes, current smoking, total cholesterol, HDL cholesterol, systolic blood pressure, and treatment for hypertension (defined from diagnosis codes). If cholesterol measures are not available, then body mass index may be used in place of lipids in the Framingham risk calculation; **NOTE: must have at least one prior encounter within 365 days within health system prior to index**
- (4) Presence of a modifiable risk factor: hypertension, diabetes, elevated total cholesterol, elevated LDL cholesterol and/or tobacco use.

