## 12 Data analysis & statistical considerations

#### 12.1 Analysis Plan for Aim 1

For this aim, the primary outcome variable is referral to a cardiology specialist within 6 months of baseline. This will be measured as a binary variable, with 'yes' defined if there is documented evidence that a referral is made within 6 months of becoming eligible by CVD risk score and kept within 3 months of referral, and 'no' otherwise. We will also determine the time from baseline to cardiology referral and the time until the first visit with the cardiology specialist.

We will consider a number of patient and provider factors evaluated at baseline that are potentially associated with referral to a cardiology specialist. Patient factors will include demographic factors (age, sex, race, ethnicity), level of ASCVD risk, Charlson comorbidity index, SES (e.g.; 5 digit zip code, health insurance ([yes/no]), type of health insurance (Medicare, Medicaid, private, Ryan White, etc.), and history of keeping appointments during 2 years prior to baseline. Provider factors will include primary management strategy (coprimary management defined as having both an HIV doctor and Primary Care Practitioner vs. HIV provider as primary care), and years of practice since training. Cardiologist availability will be a site-determined variable. Based on prior literature, we are specifically considering sex as a biological variable that may be related to specialty referral. 

Baseline characteristics of the cohort will be summarized overall and by referral status. We will include the patient and provider factors described above, as well as vital signs (including weight, body mass index and blood pressure), laboratory measures (particularly total and HDL cholesterol, CD4 cell count, HIV viral load), and relevant medications (ART and cardiovascular medications). We will document the patterns of HIV related CVD comorbidity in the study population, as the funding opportunity announcement specified.

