Univariable and multivariable logistic regression analysis will be used to identify factors that are most strongly associated with cardiology referral. The patient and provider factors listed above are of primary interest and will be included as covariates in the regression models. Subgroups of primary interest will be defined by race/ethnicity (e.g., Non-Hispanic Black, Hispanic Black, Other) and by Insurance Status (None, Medicare, Medicaid, private, Ryan White, etc.). Univariable and multivariable associations will be reported stratified by sub-groups, and reported with interaction tests between the subgroup and other factors. Statistical significance will be determined at the two-sided 0.05 level.

We will also consider a number of sensitivity analyses to evaluate robustness of our study results to various assumptions. For example, to evaluate the impact of drop-outs we will re-run analyses only including patients with routine follow-up within the health care system (e.g., as evidenced by a certain number of visits during the study period). In another sensitivity analysis, we will extend the period for counting a cardiologist referral from 6months to 12 months. If there are subgroups of patients where referral is extremely common (e.g., very high ASCVD risk) or extremely uncommon (e.g., uninsured patients) then we will evaluate the effect of excluding these subgroups in additional sensitivity analyses.

## 12.1.1 Expected power and sample size for Aim 1

Aim 1 expected power and sample size: Preliminary counts collected from sites suggest that we will identify at least 6,000 adult PLWH of Black/African-American and other URM race/ethnicity. We anticipate that 20-25% of these patients will meet the ASCVD risk threshold and be eligible for inclusion in the population for Aim 1, for an anticipated sample size of 1,200-1,500 patients. Preliminary data from our EHR and clinical experience suggests that 20-25% of those at elevated risk will have been referred to a cardiologist. This would provide at least 80% power to detect an association between cardiology referral, and a binary risk factor with 0.33 incidence, when the odds ratio for the association is 1.6 or greater. With 1,500 eligible patients the power to detect an association with an odds ratio of 1.5 would be >85%.

#### 12. 2 Analysis Plan for Aim 2

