For this aim, the primary outcome variable will be blood pressure control based on prevailing guidelines during the study period (blood pressure <140/90 mmHg). The co-primary outcome is lipid control, defined by prevailing guidelines during the study period. These outcomes will be evaluated longitudinally during 5-years of follow-up. Secondary outcome variables include time to the first major adverse cardiovascular event (MACE = cardiovascular death, myocardial infarction (MI)), stroke, heart failure hospitalization, peripheral artery disease procedure, coronary artery disease (based on diagnosis codes or coronary artery revascularization procedure), and all-cause death. Events ascertained from relevant diagnosis and procedure codes, and from a query of the National Death Index Plus, State Death records, Social Security Death Masterfile, Hospital death record and/or similar death record for causes of death including cardiovascular

death. We will also evaluate time to BP control and time to lipid control among patients who were not controlled at study start. For this Aim, "time zero" for the matched patient pair will be defined as the time from baseline (see Aim 1) when the referred patient kept their cardiology appointment. Events will be ascertained starting from time zero and until the end of follow-up. For each patient, end of follow-up will be defined as the date of the last outcome event or health system encounter without an event, occurring ≥3 months prior to the retrospective study review period of December 31, 2020 of the EHR.

To evaluate the association between cardiology referral and subsequent blood pressure and lipid control (coprimary outcomes), we will first evaluate these measures between referred and non-referred patients at baseline, and then compare prevalence and time trends between referred and non-referred patients using methods appropriate for longitudinal data analysis. For example, we will explore whether the proportion of patients with adequately controlled BP at each year is higher in referred compared to non-referred patients. Because these analyses are conducted in the matched population, the results are adjusted for the potential confounders included in the identification of the matched pairs.

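### Leaving the health system before a kept cardiology visit counts as non-referral in Aim 1, so factors linked to leaving can look like barriers to referral

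*Combined protocol and SAP*

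**What the plan says.** Section 12.1 makes the Aim 1 outcome binary: "the primary outcome variable is referral to a cardiology specialist within 6 months of baseline". A yes needs a documented referral in that window that is "kept within 3 months of referral, and 'no' otherwise". A yes can therefore take up to 6 + 3 = 9 months to appear.

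The model is logistic: "Univariable and multivariable logistic regression analysis will be used to identify factors that are most strongly associated with cardiology referral". Health insurance and history of keeping appointments are among the listed patient factors, and insurance status also defines a subgroup of primary interest.

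On observation time, inclusion criterion 3 in section 7.3.1 looks backwards only: a patient "must have at least one prior encounter within 365 days within health system prior to index". Nothing is required after index. Section 12.2 defines an end of follow-up for Aim 2 ("end of follow-up will be defined as the date of the last outcome event or health system encounter without an event"), but section 12.1 has no such date, no censoring rule and no statement about death.

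Two other items in section 12.1 bear on this. Times are recorded ("We will also determine the time from baseline to cardiology referral and the time until the first visit with the cardiology specialist"), but no model is named for them. One sensitivity analysis addresses drop-out: "to evaluate the impact of drop-outs we will re-run analyses only including patients with routine follow-up within the health care system". Its visit threshold is left open.

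**The concern.** Consider two patients without a kept visit. One stays in the system for nine months and is never referred. The other moves to a different health system at month two. Both are coded no. For the second, the record cannot show what happened later, and a logistic model on a yes/no outcome cannot use the two months that were seen.

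If leaving is equally common at every level of a factor, that factor's null odds ratio stays at 1. If leaving is more common at one level, that level shows fewer documented kept visits even when referral practice is the same. Section 4 names health insurance as its example of a patient-level factor, so this would affect a headline result: a barrier to referral could partly be a marker of loss from care. Section 12.2 then uses Aim 1 associations to help choose the Aim 2 matching factors.

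**Working it through.** **The plan's own figures.** Section 12.1.1 gives N = 1,200-1,500, referral 20-25%, factor prevalence 0.33 and two-sided alpha 0.05. Solve p0 and p1 so that 0.67·p0 + 0.33·p1 equals the overall rate at the stated odds ratio. Power = Φ[(|p1 − p0| − 1.96·SE0)/SE1], with SE0 pooled and SE1 unpooled.

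- N = 1,200, OR 1.6: 20% referral gives 0.1742 v 0.2524 and power 87.9%; 25% referral gives 92.1%. The stated minimum of 80% is met.
- N = 1,500, OR 1.5: 20% referral gives 0.1778 v 0.2450 and power 85.5%; 25% referral gives 90.2%. The stated figure of more than 85% is met.

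These figures reproduce, but they treat every outcome as observed.

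**Effect of loss on a factor with no true effect.** Observed yes rate = r·(1 − φ·L), where r is the true rate of kept referral, L the share who leave, and φ the share of leavers' would-be visits that fall after they leave. Take r = 0.225, the middle of the plan's range. L and φ are assumptions; the documents give neither. Loss without the factor is set at 5%.

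With φ = 0.5 the reference rate is 0.225 × 0.975 = 0.2194, odds 0.2810.

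| Loss with the factor | Observed rate | Odds | OR, φ = 0.5 | OR, φ = 1 |
|---|---|---|---|---|
| 5% | 0.2194 | 0.2810 | 1.00 | 1.00 |
| 10% | 0.225 × 0.95 = 0.2138 | 0.2719 | 0.97 | 0.93 |
| 20% | 0.225 × 0.90 = 0.2025 | 0.2539 | 0.90 | 0.81 |
| 30% | 0.225 × 0.85 = 0.1913 | 0.2365 | 0.84 | 0.69 |

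The rate and odds columns are for φ = 0.5. For φ = 1 the reference rate is 0.225 × 0.95 = 0.2138, and the other rates are 0.2025, 0.1800 and 0.1575.

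**Chance of a false significant result towards lower referral** (nominal 2.5%; N 1,200-1,500, referral 20-25%, prevalence 0.33), against 5% loss without the factor:

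- 10% loss: 3.9-4.5% at φ = 0.5; 6.0-7.6% at φ = 1.
- 20% loss: 9-12% at φ = 0.5; 24-37% at φ = 1.
- 30% loss: 18-27% at φ = 0.5; 58-80% at φ = 1.

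**Why the planned checks do not settle it.** The drop-out analysis keeps patients with enough visits during the study period. A kept cardiology visit is itself a visit. With a threshold of k, a patient with k − 1 other visits is retained if referred and removed if not, so selection depends on the outcome. The analysis also does not mention death and leaves the primary result unchanged. The other planned variation, counting referrals up to 12 months, lengthens the window and so exposes it to more loss.

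**The case against.** Several points on the other side stand.

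- A reader might infer that everyone who dies or leaves within nine months becomes a no. That is not so: a patient who keeps the visit and then leaves or dies is a yes. Only exits before a kept visit matter.
- A reader might infer that deaths are misclassified. A patient who dies without a kept referral did not have one, so no is correct for the probability of a kept referral. What is missing is a statement that this is the quantity being estimated.
- The bias depends on unequal loss. That insurance or appointment history predicts leaving is plausible, but the documents do not show it. At 10% v 5% loss the shift is minor, and even 0.84 is well short of the effects the study is powered for (1/1.6 = 0.63, 1/1.5 = 0.67).
- The multivariable model includes appointment history over the two years before baseline, a marker of retention. This may partly adjust the insurance odds ratio. It does not protect the odds ratio for appointment history itself.
- The plan does recognise drop-out, and its sensitivity analyses are introduced as examples.
- A time-to-event model has its own weakness. It assumes that leaving is unrelated to referral given the covariates, and a patient never seen after index contributes no time.

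It can also be argued that, because the outcome requires the appointment to be kept, disengagement is part of what Aim 1 measures. That is a legitimate estimand, but the plan does not state it. It also differs from treating a move to another health system as evidence of no referral.

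**Conclusion.** The concern holds in a limited form. The Aim 1 coding counts exit before a kept visit as non-referral, and the one drop-out check selects on something that a kept referral can raise. For a factor with no true effect, the odds ratio would be about 0.97, 0.90 or 0.84 at 10%, 20% or 30% loss against 5%, given 22.5% referral and half of leavers' would-be visits missed. If all were missed, the values would be 0.93, 0.81 and 0.69. The loss rates are assumed, so the actual size is unknown until losses are counted.

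Two stronger conclusions are not supported. The documents do not show that the Aim 1 odds ratios are biased, because they give no loss rates and equal loss leaves a null odds ratio at 1. Nor do they call for replacing the logistic model: the Aim 1 power statement is in odds ratios, and section 12.2 uses the same binary variable as the Aim 2 exposure. This is an inexpensive improvement to a sensitivity analysis, with a needed statement of the estimand.

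**What to change.** 1. Keep the binary outcome and logistic model as primary. Add a sentence stating the estimand: the probability of a kept referral within the window, with a death before a kept visit counted as no, and how exit before a kept visit is treated.
2. Replace or supplement the visit-count restriction with a named sensitivity analysis of time from index to kept cardiology visit. Use a cause-specific Cox model with the section 12.1 definition of a kept referral, censoring at the earlier of last health-system encounter and nine months, with death as a competing event. Inverse-probability-of-censoring weights in the logistic model are an acceptable alternative and keep the odds-ratio scale.
3. Report the numbers lost and dead before nine months by insurance status.

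Restricting the logistic model to patients observed through nine months is not a good substitute. It also selects on presence after baseline, and a late cardiology visit helps a patient qualify.

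The cost is plan wording, one extra model and one table. The times are already to be determined, section 8.1 provides for death linkage, and the Aim 2 last-encounter rule can be adapted. The Cox option puts hazard ratios beside odds ratios, and both options assume that leaving is non-informative given the covariates; the plan should say so.

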Then, DCRI will take the query data that the sites provide to identify and further stratify data for potential cohort of patients, based on additional clinical characteristics. At the earliest clinical contact within look back period, we will identify HIV status according to ICD9/10 codes and prescription of ART. We will include individuals >18 years of age and < 99 years of age, plus will ascertain time-updated data for the following potential characteristics:

hemoglobin, creatinine (or glomerular filtration rate), age, sex, race, ethnicity, insurance status, total cholesterol, HDL cholesterol, LDL cholesterol, systolic blood pressure, prescription of anti-hypertensive medications, family history of coronary artery disease, presence of diabetes, previous diagnosis of any acute myocardial infarction, hospitalization for heart failure, acute coronary syndromes, stable or unstable angina, arterial revascularization, stroke, transient ischemic attack and peripheral arterial disease presumed to be of atherosclerotic origin determined by ICD9/10 codes. Behavioral factors are smoking status, number of clinic visits per year, length of time between clinic visits and missed appointments with specialist after referral. Data will also be ascertained on HIV viral load, CD4 count, prescription of any ART and length of time on all medications. This list captures the majority of the data related to our scientific aims and will be modified as the availability of these data are discovered.

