Starting with the population selected for Aim 1, we will create a sub-population by matching patients referred to a cardiology specialist (the primary outcome variable for Aim 1) to similar non-referred patients. The goal of this matching is to balance factors that may be confounders of the relationship between referral and cardiovascular outcomes. We will identify factors found to be associated with cardiology referral from Aim 1, as well as factors that are expected to be associated with outcomes such as, age, race, insurance status/type, ASCVD risk score, and comorbidity index. We will not seek to match on factors that may be associated with referral but unlikely to be directly associated with outcomes. For example, we may not want to match on cardiologist availability by site if this is only related to referral and not independently to outcomes. Variables that potentially modify the effect of referral (e.g., sex, race/ethnicity, insurance status) will be included among the matching factors. Patients will be matched within sites and year of baseline encounter.

For each patient referred to a cardiologist we will identify one non-referred patient (1:1 matching) within each site. We will match using values of the individual confounders, with an exact match on sex, race/ethnicity, insurance status/type, and to within a small caliper for continuous variables (e.g., ±5 years for age). Matched pairs will be identified using optimal matching. If this approach fails to identify an adequate number of matched pairs, then 1:1 matching will be implemented using a propensity score.

Once the matching has been implemented, the same baseline characteristics reported for Aim 1 will be summarized in the matched cohort by referral status. Metrics (e.g., standardized differences) will be reported to evaluate how well-balanced the referred and non-referred groups.

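### CD4 count and HIV viral load are collected and tabulated, but nothing in the plan ensures that the Aim 1 or Aim 2 analyses adjust for them

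*Combined protocol and SAP*

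**What the plan says.** Section 8.1 makes the HIV markers part of the extraction: "Data will also be ascertained on HIV viral load, CD4 count, prescription of any ART and length of time on all medications".

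Section 12.1 defines the candidate predictors of referral: "Patient factors will include demographic factors (age, sex, race, ethnicity), level of ASCVD risk, Charlson comorbidity index", followed by socioeconomic measures, insurance and appointment-keeping history, and then by provider factors. None of these is an HIV marker. The next paragraph, on the baseline table, adds further items: "We will include the patient and provider factors described above, as well as vital signs (including weight, body mass index and blood pressure", and then "laboratory measures (particularly total and HDL cholesterol, CD4 cell count, HIV viral load), and relevant medications (ART and cardiovascular medications". For the regression it says "The patient and provider factors listed above are of primary interest and will be included as covariates in the regression models".

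Section 12.2 gives two routes into the match. The first is empirical: "We will identify factors found to be associated with cardiology referral from Aim 1". The second rests on expected prognosis: "factors that are expected to be associated with outcomes such as, age, race, insurance status/type, ASCVD risk score, and comorbidity index". The mechanics are an "exact match on sex, race/ethnicity, insurance status/type, and to within a small caliper for continuous variables", with age as the one worked example and a propensity score as fallback. After matching, the Aim 1 baseline characteristics are tabulated again with balance metrics. The BP and lipid results are then treated as adjusted because the cohort is matched, and the Cox models name no term apart from referral status and the subgroup interactions.

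**The concern.** The exposure is not simply being referred. Section 12.1 counts a patient as referred only if the referral was made in the six months after eligibility and was attended within three months of being made. That definition favours patients who engage with care. Every patient has an ART prescription (section 7.3.1), so viral load is a laboratory marker of whether treatment is being taken. The same behaviour plausibly affects BP control, lipid control and survival. The opposite pattern is also plausible: patients with more advanced HIV disease may be sent to cardiology more often.

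If HIV control differs between the matched groups, part of any difference in outcome could reflect HIV care and not cardiology care. For Aim 1, the specified model would give no adjusted association between HIV control and referral, only the unadjusted comparison in the baseline table.

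**Working it through.** **Where the two markers appear, stage by stage**

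- Extraction (8.1): both are named.
- Baseline table by referral status (12.1): both are named, as an addition to the patient and provider factors.
- Aim 1 regression (12.1): the specified covariates are the patient and provider factors; neither marker is among them.
- Match, first route (12.2): a variable outside the Aim 1 models cannot be found associated with referral by those models.
- Match, second route (12.2): neither named nor excluded, since the list is given as examples.
- Post-match balance table (12.2): both are included, because the Aim 1 table is repeated. No action is tied to the result.
- Outcome models (12.2): neither is named.

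**The plan's own power figures (12.2.1)**

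Inputs: 300 per group, two-sided 0.05, BP control 30% vs 40%, lipid control 45% vs 60%. Power = Φ[(d − 1.96·SE0)/SE1], where SE0 uses the pooled rate.

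- BP: SE0 = √(2 × 0.35 × 0.65/300) = 0.0389; SE1 = √((0.21 + 0.24)/300) = 0.0387; power = Φ[(0.10 − 0.0763)/0.0387] = 72.9%. The plan states more than 70%.
- Lipids: the same formula gives 95.9%. The plan states more than 95%.

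Both reproduce. Neither depends on whether HIV markers are matched.

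**Possible size of the bias in BP control**

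The documents give no figure for the link between HIV control and referral, or between HIV control and outcome. The inputs below are assumptions, taken over a range.

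Bias = (difference in prevalence of HIV control between matched groups) × (difference in BP control between patients with and without HIV control).

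The false-positive rate is for no true effect, with 30% against 30% plus the bias. The last column is the power when the bias works against a true 10-point gain.

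| Assumed gap × effect (points) | Bias (points) | False-positive rate | BP power, adverse bias |
|---|---|---|---|
| none | 0 | 5.0% | 72.9% |
| 5 × 5 | 0.25 | 5.05% | 70.8% |
| 10 × 10 | 1.0 | 5.8% | 64.1% |
| 20 × 15 | 3.0 | 12.4% | 44.3% |
| 20 × 20 | 4.0 | about 18% | 34.5% |

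**All-cause death (secondary), illustrative**

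With no true effect, the spurious hazard ratio is (p1 + (1 − p1)h)/(p0 + (1 − p0)h). Here p1 and p0 are the proportions suppressed among referred and non-referred patients, and h is the death hazard of unsuppressed relative to suppressed patients. Taking p0 = 0.70:

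- p1 = 0.80, h = 2: 1.2/1.3 = 0.92
- p1 = 0.80, h = 3: 1.4/1.6 = 0.875
- p1 = 0.85, h = 3: 1.3/1.6 = 0.81

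If referred patients were the less suppressed group, the ratio would exceed 1.

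**Cost of forcing the markers into the match**

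If stricter matching cut the cohort from 300 to 250 pairs, power would fall from 72.9% to 65.0% for BP and from 95.9% to 92.1% for lipids.

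**The case against.** The strongest reply is that the plan omits detail but does not exclude these variables. The prognostic route in 12.2 is open-ended and the stated purpose of matching is to balance confounders, so anyone who believes viral suppression predicts outcome may add it under the plan's own rule. Section 12.1 does not say that its listed factors are the only covariates. This stands: a reader might infer that the plan shuts HIV markers out of every model and match, and the text does not go that far.

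Second, engagement with care is partly covered. Appointment-keeping over the previous two years is an Aim 1 covariate and is close to the behaviour built into the exposure. Matching is exact on insurance type and is done within site and baseline year. Everyone has an ART prescription. The sensitivity analysis limited to patients in routine follow-up carries over to Aim 2. This stands in part. Appointment history is not among the named outcome predictors, so its assured way into the match is an association found in Aim 1. It needs two years of data, whereas section 8.1 gives a one-year look-back and section 7.3.1 requires only one earlier encounter within 365 days. Attendance is also not the same as viral suppression, and an ART prescription does not equalise HIV control.

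Third, the repeated baseline table would reveal an imbalance. It would, but no adjustment follows from it.

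Fourth, the magnitudes are assumed and are not conditioned on the other matching factors. That stands. The middle case (10 × 10) moves the false-positive rate only from 5.0% to 5.8%, and the highest figure needs both inputs at their maximum.

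**Conclusion.** The plan does not ensure control for HIV disease status in either aim, and residual confounding of the Aim 2 comparison is possible. A reader might go further and conclude that HIV control does confound Aim 2, or that a benefit of referral would be an artefact of better HIV care. The documents do not support that. They contain no figure for either link, the direction could go either way, and the other matching factors may absorb part of it.

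Under the assumed range the bias in BP control runs from negligible (0.25 points) to material (4 points, or 40% of the planned 10-point effect). The conclusion rests on three things: the natural reading that the laboratory measures are separate from the patient and provider factors; the absence of any required adjustment after the balance check; and the plausibility, not shown in the documents, that HIV control relates both to keeping a referral and to outcome. No stated power figure is wrong. The change is worth making because the data are already extracted and the adjustment is nearly free.

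**What to change.** In 12.1, add baseline viral suppression (yes/no) and CD4 category to the patient factors in the Aim 1 logistic model. Take the last value on or before index, so that nothing measured after referral enters. State a rule for missing values, for example a separate not-measured level. Section 12.2 refers to Aim 1 for missing data, but 12.1 gives no rule for missing covariates.

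In 12.2, include both variables in the propensity score if the fallback is used. Otherwise enter them as covariates in the longitudinal BP and lipid models and in the Cox models, keeping the sandwich variance for pairs in the latter. Do not make them exact-match variables, so that pairs are not lost.

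Standardized differences for these variables are already planned and need no change. The cost is wording, a few more model terms and some missing laboratory values. In return, Aim 1 can report an adjusted association between HIV control and referral.
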